### Treatment Phase (12 weeks)

Subjects who complete all of the screening assessments will return to the clinic on Treatment Day 1 (Baseline) to repeat laboratory tests and physical assessments. Subjects who continue to be eligible will be enrolled to receive MN-001 250 mg qd (250 mg/day) for 4 weeks and will take 250 mg bid (500 mg/day) for 8 weeks.

Subjects will receive their first dose of study medication on Day 1 at the clinic. The first 6 subjects will have the option to stay at the study center overnight on Day 1 or return to the clinic the following day for the last/final blood draw. Blood samples for MN-001 /MN-002 (major metabolite) concentrations will be collected at the following timepoints:

- Day 1
  - o Baseline: prior to the first dose
  - o post dose hour 0.5, 1.5, 3, 6, 9, 12, 24\* (\*Day 2)

PK parameters will be calculated and results will be reviewed prior to increasing the dose to 250 mg bid after Week 4.

Subjects will return to the clinic at Weeks 4, 8, and 12. After Week 4, subjects will start taking 250 mg bid. During these visits, subjects will undergo safety and efficacy assessments. ECGs will be conducted at  $T_{max}$  at hour 1.5 (± 30 minutes) after drug ingestion at each clinic visits: See Table 1 for visit schedule and procedures for all assessments.

Throughout the Treatment Phase, safety parameters will be assessed and concomitant medications will also be documented. The safety and tolerability of MN-001 will be evaluated by an Independent Safety Monitor during this phase.

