#### Sample Size Justification:

The sample size is not based on hypothesis testing. The selected sample size is considered adequate to provide a preliminary evaluation of efficacy and safety.

Phase	Scre	eening	Treatment			Follow-up		
Tests and Evaluations	Day -120 to Day -7	– 1 week ± 5 days	Baseline Day 1-2*	Week 2 ± 3 days	Week 4 ± 5 days	Week 8 ± 5 days	Week 12/ET** ± 5 days	Week 13 ± 5 days
Type of Visit	Clinic	Lab	Clinic	Tel	Clinic	Clinic	Clinic	Clinic
Study Visit Number	1	2	3	4	5	6	7	8
Informed consent	Х							
Inclusion/exclusion criteria review	Х		Х					
Medical history	Х							
Physical examination	Х		Х		Х	Х	Х	Х
Body height	Х							
Body weight/Waist circumference	Х		Х		Х	Х	Х	Х
Vital signs	Х		Х		Х	Х	Х	Х
Alcohol consumption questionnaire	Х						Х	
Pregnancy test (serum /urine)	X (serum)	X (serum)			Х	Х	Х	
12-lead ECG	Х		Х		Х	Х	Х	
Clinical labs (chemistry, incl CPK, hematology, lipid panel coagulation profile including INR, urinalysis)	Х	Х			Х	X	Х	Х
CK-18 biomarker	Х						Х	
Fib-4 Index calculation	Х							
NAFLD fibrosis score	Х							
Blood Sample for Cholesterol Efflux			Х				Х	
MN-001 plasma concentration ***			Х					
Liver MRI a	X****						X****	
Adverse event review			Х	Х	Х	Х	Х	Х
Concom med review	X		Х	Х	Х	Х	X	
Study Drug Dispensing			Х					
Study Drug Accountability				X	Х	Х	Х	

\* Baseline visit will be overnight stay for selected 6 subjects from whom PK samples will be obtained

\*\* ET: Early termination visit

\*\*\* PK sample for MN-001/002 will be also obtained when subjects experience SAE \*\*\*\* Liver MRI can be scheduled on different day of each lab/clinic visit

a Pre-treatment Liver MRI may be performed between Day -120 and Day -1prior to Baseline Day 1

MEDICINOVA, INC.

2.	TABLE OF CONTENTS	
1.	SYNOPSIS	3
2.	TABLE OF CONTENTS	10
3.	LIST OF ABBREVIATIONS AND DEFINITIONS OF TERMS	14
4.	BACKGROUND AND RATIONALE	17
4.1.	Introduction	17
4.1.1.	Rationale of the MN-001 for treatment of NASH and NAFLD Subjects with hypertriglyceridemia	18
4.2.	Prior Clinical Experience	19
4.2.1.	Clinical Study Overview	19
4.3.	Potential Drug-Drug Interactions	24
5.	TRIAL OBJECTIVES AND PURPOSE	26
5.1.	Primary Objectives	26
5.2.	Secondary Objectives	26
6.	OVERALL STUDY DESIGN AND PLAN: DESCRIPTION	27
6.1.	Screening Phase (up to - 4 months to - 7 days)	27
6.1.1.	Diagnosis at Screening	27
6.1.2.	Treatment Phase	28
6.1.3.	Follow-up Phase	28
7.	SELECTION AND WITHDRAWAL OF SUBJECTS	29
7.1.	Clinical Trial Population	29

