# 7.2. Inclusion/Exclusion Criteria

### 7.2.1. Inclusion Criteria

- Written informed consent is obtained and willing and able to comply with the protocol in the opinion of the Investigator.
- Male or female subjects  $\geq 18$  years of age
- Histologically proven NASH (NAFLD activity score of 3 or greater with at least 1 point being ballooning) based on liver biopsy performed within the last 36 months or NAFLD confirmed by imaging studies.
- Fasting serum triglyceride level > 150 mg/dL (confirmed at screening)
- Serum ALT, AST, ALP and total bilirubin levels at Screening (- 120 days to -30 days) and Lab Visit values (- 1 week ± 5 days) are stable or changes at the Lab visit are < 20% of the values from Screening.
- Subjects on the following medications can be enrolled if these medications are necessary, cannot be stopped, and the dose has been stable for 4 months or more prior to baseline:
  - Stable doses of anti-diabetic medications
  - Stable doses of fibrates, statins, niacin, ezetimibe.
  - Stable doses of Vitamin E for at least 8 weeks
- Less than 21 units of alcohol/week for men and 14 units of alcohol/week for women over a 2-year time frame
- Females of child-bearing potential must have a negative serum ß-hCG at screening and must be willing to use appropriate contraception (as defined by the investigator) for the duration of study treatment and 30 days after the last dose of study treatment.
- Males should practice contraception as follows: condom use and contraception by female partner.
- Subject is in good physical health on the basis of medical history, physical examination, and laboratory screening, as defined by the investigator.
- Subject is willing and able to comply with the protocol assessments and visits, in the opinion of the study nurse/coordinator and the Investigator.

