# 8.8.1.2. Treatment Phase (12 weeks)

Subjects who complete all of the screening assessments will return to the clinic on Treatment Day1 (Baseline) to repeat laboratory tests and physical assessments. Subjects who continue to be eligible will be enrolled to receive MN-001 250 mg qd for 4 weeks and then increase their dosage to 250 mg bid (500 mg/d) for the remaining 8 weeks (total dosing of 12 weeks). Subjects will receive their first dose of study medication on Day 1 at the clinic.

Subjects will enter the clinic in the morning prior to breakfast. Once the pre-dose fasting labs have been completed, subjects will be given breakfast.

### Visit 3: Baseline Day 1

- Inclusion/Exclusion review
- Body weight/waist circumference
- Vital signs
- Physical Examination
- 12-lead ECG at hour 1.5 (± 30 minutes) post dose
- Blood sample for Cholesterol efflux capacity test
- MN-001 blood concentration sample will be collected at the following timepoints: prior to the first dose and at Hour 0.5, 1.5, 3, 6, 9, 12 and 24 (± 30 minutes) post dose for the first 6 subjects only\*
- Concomitant medication review
- Adverse event review
- Dispense study drug

Once the pre-dose assessments have been completed, the subject will be administered a single dose of MN-001 with room temperature water.

\* The first 6 subjects enrolled in the study will have the option to remain in the clinic overnight until the last PK blood sample is drawn or return the following day for the last/final blood draw.

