# **10. ASSESSMENT OF EFFICACY**

#### **10.1. Primary Endpoints**

The primary endpoint, cholesterol efflux, will be calculated as the percent of cholesterol removed from the cells and appearing in the culture medium normalized to a reference serum pool. The ability of serum HDL to remove cholesterol from cultured cells will be assessed as an *in vitro* method to evaluate functional changes in HDL mediated by changes due to MN-001 treatment.

Cholesterol efflux with HDL will be measured by Cholesterol Efflux Fluorometric Assay Kit (BioVision, Inc.). Detailed protocol is attached in Appendix 3.

An additional primary endpoint is will evaluate the effects of MN-001 on triglyceride level in subjects with NAFLD or NASH. The primary endpoint will be decreased triglycerides measured as the difference after 12 weeks of treatment from baseline levels. The data are expressed as the percent change from the baseline value and calculated using he equation: Change = [100%\*(Endpoint value - Baseline Value)/Baseline Value]

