### 6.2 Study Endpoints (Outcome Variable)

### **Co-Primary Outcome Variables**

• Mean change from baseline on serum triglyceride levels at Week 8

The primary endpoint is to evaluate the effects of MN-001 on serum triglyceride level in NASH and NAFLD with hypertriglyceridemia. The serum triglycerides will be measured as the difference after 8 weeks of treatment from pre-treatment serum triglyceride levels. Pre-treatment triglyceride level will be defined as the highest value of serum triglyceride at screening visit or baseline visit. The data are expressed as the percent change from the baseline value and calculated using he equation: Change = [100%\*(Endpoint value - Baseline Value)/Baseline Value]

• Mean change from baseline on cholesterol efflux capacity at Week 12

Cholesterol efflux capacity in the subjects will be quantified at National Institute of Biomedical Innovation, Osaka, Japan using the method previously reported (Ogura et al 2016). Percent efflux will be calculated by the following formula:  $[(\mu Ci of 3H-cholesterol in mediums containing 2.8% apolipoprotein B-depleted serum -\mu Ci of 3H-cholesterol in serum-free mediums)/\mu Ci of 3H-cholesterol in cells extracted before the efflux step] × 100. All assays will be performed in duplicate. To correct for inter-assay variation across plates, a pooled serum control from eleven healthy volunteers was included on each plate, and values for serum samples from patients were normalized to the value of the pooled sample in subsequent analyses.$ 

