# **11 EFFICACY ANALYSIS**

### 11.1 Serum Triglyceride Level

The primary endpoint is to evaluate the effects of MN-001 on serum triglyceride level in NASH and NAFLD with hypertriglyceridemia. The serum triglycerides will be measured as the difference after 8 weeks of treatment from pre-treatment serum triglyceride levels. Pre-treatment triglyceride level will be defined as the highest value of serum triglyceride at screening visit or baseline visit. The data are expressed as the percent change from the baseline value and calculated using the equation: Change = [100%\*(Endpoint value - Baseline Value)/Baseline Value].

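### The SAP moves the triglyceride primary endpoint from 12 weeks to Week 8 without a reason, and its highest-value baseline, where two pre-treatment values exist, can only push the change downward

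*Combined protocol and SAP*

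**What the plan says.** **Time point.** Protocol 10.1 states: "The primary endpoint will be decreased triglycerides measured as the difference after 12 weeks of treatment from baseline levels", expressed as percent change. SAP 6.2 names the co-primary variable as "Mean change from baseline on serum triglyceride levels at Week 8", and SAP 6.2 and 11.1 both state: "The serum triglycerides will be measured as the difference after 8 weeks of treatment from pre-treatment serum triglyceride levels". Table 14.2.1 and Listing 16.2.6.1 are also Week 8. The other co-primary, cholesterol efflux, stays at Week 12. For secondary lipids and liver enzymes, protocol 10.2 says Week 12, and SAP 11.3 and Listing 16.2.6.3 cover both weeks, but Tables 14.2.2 and 14.2.3 are Week 8 only.

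**Baseline.** The protocol refers to baseline levels without naming a draw. SAP 6.2 and 11.1 supply a rule: "Pre-treatment triglyceride level will be defined as the highest value of serum triglyceride at screening visit or baseline visit".

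**Which draws exist.** The Synopsis and protocol 8.8.1.2 say that subjects "will return to the clinic on Treatment Day 1 (Baseline) to repeat laboratory tests and physical assessments", and 8.8.1.2 adds: "Once the pre-dose fasting labs have been completed, subjects will be given breakfast". However, Table 1 in both documents marks clinical labs at Screening and -1 week and not on Day 1, and the Visit 3 list in 8.8.1.2 has no clinical labs. Protocol 6.1.2 and the Visit 2 entry in 8.8.1.1 put the repeat labs about one week before Day 1.

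**Entry and design.** Entry requires fasting triglycerides > 150 mg/dL, confirmed at screening (7.2.1). The study is open-label with one arm.

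**The concern.** The two documents give different primary endpoints for the same variable. Under the planned schedule, Week 8 falls halfway through the second dose step, so the two time points measure different exposures. A reader of Table 14.2.1 would not get the quantity that the protocol calls primary.

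The baseline rule is a separate problem. In a single-arm study the whole apparent effect is the difference between baseline and endpoint. Choosing the larger of two noisy pre-treatment readings raises the baseline without changing the endpoint, so some decrease would appear even with an inactive drug. SAP 8.1 says the results will be used to design future studies. An inflated fall would carry over into those designs.

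**Working it through.** **1. Time point.** Protocol 10.1 says 12 weeks. SAP 6.2, SAP 11.1, Table 14.2.1 and Listing 16.2.6.1 say Week 8. Four agreeing places are not a slip of the pen. All three efficacy tables in SAP 15.1 are Week 8 and none is Week 12, yet Week 12 lipids are scheduled.

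Days at the second dose step (increase at day 28 ± 5, visits ± 5 days):
- Week 8: 56 - 28 = 28 days, range 51 - 33 = 18 to 61 - 23 = 38.
- Week 12: 84 - 28 = 56 days, range 79 - 33 = 46 to 89 - 23 = 66.

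**2. The formula.** Both documents use 100 × (Endpoint - Baseline)/Baseline. Applied to the 11 prior-study triglyceride rows in protocol 4.2.1, it reproduces each printed percentage within 0.1 point, for example 100 × (87.5 - 145.4)/145.4 = -39.8%.

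**3. Direction.** max(X1, X2) is at least X1 and at least X2. Each subject's percent change is therefore equal to or below the change from either single value. This holds for any distribution, provided two values exist.

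**4. Size with no drug effect.** The documents give no within-subject CV, so 10% to 30% is assumed. Screening, baseline and endpoint values are taken as independent and lognormal around one subject level, with s² = ln(1 + CV²).
- Highest of two, mean change: (1 + CV²) × 2 × Φ(-s/√2) - 1
- Highest of two, geometric mean change: exp(-s/√π) - 1
- One value, mean change: CV², with median and geometric mean change 0

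At CV 10%, s = 0.0998 and Φ(-s/√2) = 0.4719, so the mean is 1.01 × 2 × 0.4719 - 1 = -4.7%. At CV 30%, s = 0.2936 and Φ(-s/√2) = 0.4178, so it is 1.09 × 2 × 0.4178 - 1 = -8.9%.

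| CV | Highest of two: mean | Highest of two: geometric mean | One value: mean |
|---|---|---|---|
| 10% | -4.7% | -5.5% | +1.0% |
| 15% | -6.3% | -8.1% | +2.2% |
| 20% | -7.6% | -10.6% | +4.0% |
| 25% | -8.4% | -13.0% | +6.2% |
| 30% | -8.9% | -15.3% | +9.0% |

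Simulation with 4 million subjects per setting agrees. If the -1 week value also counted, the highest of three would give a mean of -7.4% to -16.6% over the same CVs.

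**5. Adding the entry cut.** Screening value > 150 mg/dL; assumed population median 150, 200 or 250 mg/dL; between-subject CV 40%; within-subject CV 15% or 30%; no drug effect. Ranges over the six cases:

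| Baseline used | Mean | Median |
|---|---|---|
| Highest of two | -6.8% to -15.5% | -8.4% to -20.9% |
| Screening value only | -6.4% to +3.3% | -1.1% to about -13% |
| Later draw, not used for entry | +2.2% to +9.0% | 0% |
| -1 week draw, also required > 150 | -2.4% to +4.5% | -0.7% to -9.2% |

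The second row applies if there is no Day 1 draw and the -1 week labs do not count. The fourth applies if the -1 week value must also pass the cut.

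**The case against.** **There may be only one value.** This is the strongest objection, and it stands as a condition. The schedules and the Visit 3 list show no Day 1 labs. If the screening value is the only one that counts, the rule has nothing to choose between and adds no shift. A reader might infer that the rule biases the result downward in every case; the documents do not settle that. Regression to the mean would remain, but the mean could then fall on either side of zero (-6.4% to +3.3%).

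**The size is assumed.** Correct. Positive correlation between the two pre-treatment readings would shrink it. A reader might also take the gap between the highest-value and single-value means (8.6 to 17.9 points at CV 15% to 30%) as the bias. It is not: the single-value mean is itself 2.2 to 9.0 points too high. Against a true change of zero, the shift before the entry cut is 6.3 to 8.9 points at those CVs.

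**The SAP may fill gaps.** Protocol 13 and 13.1.2 leave efficacy methods to the SAP. Defining an undefined baseline is within that remit, so the rule's absence from the protocol is not in itself a conflict. Moving a primary time point that the protocol has fixed is different.

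**Much is recoverable.** The SAP's Summary Statistics text plans medians and values at each time point, and chemistry is tabulated and listed by visit, so Week 12 values are not lost. But those are visit summaries. The percent-change primary appears in no named Week 12 output.

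**Pilot and version.** No test of triglycerides is planned and the sample size has no power basis, so the estimate itself is the product. SAP 5.1 cites protocol Amendment 3, and the supplied protocol cannot be confirmed as that version. The two supplied texts still disagree.

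**Conclusion.** The time-point conflict is established from the text and needs no assumption. A reader might infer that Week 8 was chosen because it looked better. The documents do not show when or why the change was made, so they do not support that; the defect is the missing reason.

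The baseline concern holds conditionally. Where two values exist, the direction is certain and nothing in the design offsets it. The size rests on assumed variability and independent draws: a mean of about -5% to -9% with no drug effect at CV 10% to 30%, and about -7% to -15% once the entry cut is added under the assumed populations at CV 15% to 30%. For scale, six of the seven active-arm Week 4 changes in protocol 4.2.1 are falls of 16.3% to 29.4%, so such a shift would not be negligible. If only the screening value counts, the highest-value rule is harmless but the baseline is the very reading used to select subjects.

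Both parts should be corrected before database lock. Confidence is high on the time point and on the direction, and lower on the size.

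**What to change.** 1. **Time point.** Restore Week 12 as the primary triglyceride time point in SAP 6.2 and 11.1, or keep Week 8 by a dated protocol amendment that gives the reason. Either way, report percent change at Weeks 8 and 12 in Tables 14.2.1 to 14.2.3.
2. **Baseline.** Replace the highest-value rule with one pre-specified draw: Day 1 pre-dose if it is drawn, otherwise the -1 week lab. Reconcile Table 1 and the Visit 3 list with the Synopsis, 6.1.2 and 8.8.1.2 on whether Day 1 labs exist. Protocol 6.1.2 uses the -1 week labs to confirm eligibility, and the Synopsis applies the triglyceride cut during the Screening Phase, so a draw free of selection may not exist. State that some regression to the mean remains if the chosen draw also served to confirm the triglyceride criterion.
3. **Summary.** Lead with the already planned median, or with the geometric mean ratio, because the arithmetic mean of percent changes is biased upward even with one baseline value. Keep the highest-value version as a sensitivity analysis only.
4. **Separate, smaller point.** Reconcile the efflux assay. Protocol 10.1 and Appendix 3 use a fluorometric kit, with media plus lysate as denominator. SAP 6.2 and 11.2 use 3H-cholesterol, with the label in cells before efflux as denominator.

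**Cost.** SAP wording, Week 12 columns in three tables, and a short amendment if Week 8 or the 3H assay is kept. No new visit is needed, since Week 12 lipids and the -1 week labs are already scheduled; a Day 1 sample, if wanted and not now drawn, would be an extra draw at an existing visit. The downsides are a little more table work, a less favourable triglyceride figure and possibly a few more missing values at Week 12.

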#### **Secondary Outcome Variables**

- Treatment-emergent adverse events (TEAEs) and Treatment-emergent serious adverse events (SAE);
- Discontinuations of treatment for any reason;
- Treatment discontinuations due to TEAEs;
- Treatment discontinuations due to treatment-related AEs or SAEs;
- Changes from baseline for safety clinical laboratory tests;
- Changes from baseline in vital signs and 12-lead ECG;
- Lipid profile (serum HDL-C, LDL-C, total cholesterol level), liver enzymes (ALT and AST) changes from baseline;
- Changes of liver fat content (%) assessed by MRI from baseline to post treatment MRI.

# 7 STUDY DESIGN

### 7.1 General Study Design and Plan

This is a multi-center, proof-of-principle, open-label study designed to evaluate the efficacy, safety, and tolerability of MN-001 in subjects diagnosed with non-alcoholic steatohepatitis (NASH) or NAFLD with hypertriglyceridemia. Subjects will receive MN-001 250 mg qd for the first 4 weeks and will take 250 mg bid for an additional 8 weeks. Subjects will receive MN-001 for a total of 12 weeks. Anticipated enrollment is 20-40 subjects.

### 7.2 Inclusion-Exclusion Criteria and General Study Population

Eligible subjects will consist of males and female participants  $\geq 18$  years of age. To be eligible, subjects must have a histologically confirmed diagnosis of NASH within 36 months of baseline visit or NAFLD confirmed by imaging studies and an elevated serum triglyceride (>150 mg/dL) at screening. Diagnosis of other known cause of liver disease, current diagnosis or suspicion of hepatocellular carcinoma, decompensated or severe liver disease, and uncontrolled diabetes mellitus Type 2, are major exclusionary criteria.

### 7.3 Randomization and Blinding

This is an open-label study; therefore, randomization and blinding are not applicable.

### 7.4 Study Assessments

Please see Schedule of Events in Table 1.

#### **Table 1 Schedule of Events**

Phase Screening			Treatment					Follow-up
Tests and Evaluations	Day -120 to Day -7	- 1 week ± 5 days	Baseline Day 1-2*	Week 2 ± 3 days	Week 4 ± 5 days	Week 8 ± 5 days	Week 12/ET** ± 5 days	Week 13 ± 5 days
Type of Visit	Clinic	Lab	Clinic	Tel	Clinic	Clinic	Clinic	Clinic
Study Visit Number	1	2	3	4	5	6	7	8
Informed consent	Х							
Inclusion/exclusion criteria review	Х		Х					
Medical history	Х							
Physical examination	Х		Х		Х	Х	Х	Х
Body height	Х							
Body weight/Waist circumference	Х		Х		Х	Х	Х	Х
Vital signs	Х		Х		Х	Х	Х	Х
Alcohol consumption questionnaire	X						Х	
Pregnancy test (serum /urine)	X (serum)	X (serum)			Х	Х	Х	
12-lead ECG	Х		Х		Х	Х	Х	
Clinical labs (chemistry, incl CPK, hematology, lipid panel coagulation profile including INR, urinalysis)	Х	Х			Х	Х	х	Х
CK-18 biomarker	Х						Х	
Fib-4 Index calculation	Х							
NAFLD fibrosis score	Х							
Blood Sample for Cholesterol Efflux			Х				Х	
MN-001 plasma concentration ***			Х					
Liver MRI a	X****						X****	
Adverse event review			Х	Х	Х	Х	Х	Х
Concom med review	X		X	Х	Х	Х	Х	
Study Drug Dispensing			Х					
Study Drug Accountability				Х	Х	Х	Х	

\* Baseline visit will be overnight stay for selected 6 subjects from whom PK samples will be obtained

\*\* ET: Early termination visit \*\*\* PK sample for MN-001/002 will be also obtained when subjects experience SAE \*\*\*\* Liver MRI can be scheduled on different day of each lab/clinic visit

a Pre-treatment Liver MRI may be performed between Day -120 and Day -1prior to Baseline Day 1

